7.2 Secondary Outcome Measures

Evidence of efficacy will be assessed from any improvement in visual function and reduction in macular cystic changes with respect to baseline measurements and with respect to the fellow untreated eye, herein referred to as the control eye.

The following secondary outcomes of visual function will be assessed on both the study (and control eyes where applicable):

- Change in BCVA from baseline at all time points;
- Change in the maximum subretinal fluid volume as measured on OCT at all applicable time points compared to baseline;
- Change in the central retinal thickness as measured on OCT at all applicable time points compared to baseline;

- Change in central visual field sensitivity as measured by microperimetry testing at Day 2 and Week 5 compared to baseline.

For those participants who enroll on CAIs, the effect of the addition of IFN gamma-1b on recalcitrant macular cystic changes will also be assessed.

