OHSRP	Office of Human Subjects Research Protections
OMIM	Online Mendelian Inheritance in Man
PhD	Doctor of Philosophy
PI	Principal Investigator
RCD	Rod-cone dystrophy
RN	Registered Nurse
RP	Retinitis Pigmentosa
RPE	Retinal Pigment Epithelium
SAE	Serious Adverse Event
ScM	Master of Science
SOP	Standard Operating Procedures
VA	Visual Acuity
VFQ	Visual Field Questionnaire

PRÉCIS

Objective: Rod-cone dystrophy (RCD) is a term applied to a number of genetically heterogeneous diseases presenting with night vision abnormalities, visual field defects and reduced rod electroretinography responses. Enhanced S-Cone syndrome (ESCS) is a rare autosomal recessive retinal disease with a developmental and a degenerative aspect. Macular cystic changes, often florid and usually resulting in a reduction of central acuity, are frequently associated with both diseases. The reason for this association is not well understood. Acetazolamide (Diamox) and Dorzolamide (Trusopt) have been reported to have variable success in reducing these cystic changes but the effect is frequently inadequate. The objective of this study is to evaluate the safety and potential efficacy of Interferon (IFN) gamma-1b administered topically for macular edema/retinal schisis cysts in RCD and ESCS. Possible disease-related pathophysiologic mechanisms will be explored using induced pluripotent stem cell (iPSC) protocols leading to iPSC-derived retinal pigment epithelium (RPE) and photoreceptor generation.

Study Population: Up to five participants with RCD with significant macular cystic changes and up to five participants with ESCS with significant macular cystic changes will be enrolled to receive IFN gamma-1b administered topically in one eye. However, up to an additional two participants may be enrolled in order to obtain the five participants in each disease group to be included in the primary analysis if any participants withdraw from the study prior to receiving five days of treatment.

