Design: This is a single-center, prospective, uncontrolled, unmasked pilot Phase I/II study of the safety, tolerability and possible efficacy of IFN gamma-1b in participants with RCD and ESCS and macular cystic changes. One eye of up to five participants with RCD with significant macular cystic changes and up to five participants with ESCS with significant macular cystic changes [evidenced by optical coherence tomography (OCT) >275 microns central macular thickness and/or disruption of foveal contour] will receive topical IFN gamma-1b instilled as drops on the cornea. The initial stage of the study will include two participants from each disease category. Once all four participants have completed the 8-week visit, enrollment will be halted. Safety Adverse Event Review Committee members unaffiliated with the study will review the

data as a preliminary assessment of safety and efficacy and to determine whether enrollment should continue. If the committee determines enrollment will continue, three additional participants with RCD and three participants with ESCS will be enrolled. The study will be completed once the final participant has received one year of follow-up.

Outcome Measures: The primary outcome measure related to the safety and tolerability of IFN gamma-1b administered topically at the prescribed dosage for macular cystic changes in participants with RCD and ESCS will be assessed by the number and severity of adverse events related to the IP and the number of withdrawals at 52 weeks (one year) post-administration. Additional safety of IFN gamma-1b administered topically in participants with RCD and ESCS will be determined from the assessment of retinal function, ocular structure and occurrence of adverse events at all time points. Secondary outcomes include changes in visual function including visual acuity and microperimetry, and retinal imaging with OCT and fluorescein angiography.

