3.2.1 Study Eye Inclusion Criteria

1. The study eye must retain adequate fixation to allow for completion of protocol assessments.
2. The study eye must have macular cystic changes (>275 microns and/or disruption of foveal contour on OCT).

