3.2.3 Study Eye Selection Criteria in Cases of Bilateral Disease

RCD and ESCS usually affect both eyes to a similar degree. In case both eyes of a participant meet the study eye eligibility criteria, the following criteria will be used to select the study eye:

- The eye with more intraretinal fluid will be selected as the study eye;

- If both eyes have similar levels of intraretinal fluid, the eye with worse visual acuity will be selected as the study eye;
- If both eyes have the similar levels of intraretinal fluid and visual acuities, the right eye will be selected as the study eye.

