APPENDIX 1: STUDY FLOWSHEET

Visit Schedule	Baseline	Day 1	Day 2	Day 3	Week 1	Week 2	Week 5	Week 6	Week 8	Week 52
Visit Number	000	000A	000B	000C	001	002	005	006	008	SFTY ⁸
Target Day from Baseline	0	1	2	3	7	14	35	42	56	365
Visit Window					±1 day	±5 days	±7 days	±7 days	±7 days	±30 days
Investigational Product										
Interferon Gamma-1b Dropperettes Dispensed		X ¹	X ¹	X ¹						
Drug Accountability Review						X				
General Assessments										
Medical/Ophthalmic History	X									
Brief Physical Examination	X									
Concomitant Medications Assessment	X	X	X	X		X	X		X	X
Adverse Event Assessment	X	X	X	X		X	X		X	X
Vital Signs	X	X	X			X			X	
Telephone Assessment					X			X		
Ophthalmic Assessments										
BCVA (EVA)	X	X	X	X		X	X		X	X
Manifest Refraction ²	X								X	
Slit Lamp Examination	X	X	X	X		X	X		X	X
Dilated Fundus Examination	X	X	X	X		X	X		X	X
Intraocular Pressure (IOP)	X	X	X	X		X	X		X	X
Color Vision Assessment (Cambridge Color Test)	X ³						X			
Color Fundus Photography (CFP)	X ³					X			X	
Fundus Autofluorescence (FAF)	X ³					X			X	
Lens Photography	X ³					X			X	
Optical Coherence Tomography (OCT)	X ⁴	X ⁴	X ⁴	X ⁴		X	X		X	
Fluorescein Angiogram (FA)	X ³					X				
Microperimetry	X ³		X				X		X	
Electroretinography (ERG)	X						X			
Electrooculography (EOG)	X		X			X	X		X	
NEI VFQ-25	X ³					X			X	
Research Sample Collection										
Skin Biopsy for iPSCs ⁵		X								
Blood Sample for iPSCs ⁵		X								

Visit Schedule	Baseline	Day 1	Day 2	Day 3	Week 1	Week 2	Week 5	Week 6	Week 8	Week 52
Visit Number	000	000A	000B	000C	001	002	005	006	008	SFTY ⁸
Laboratory Testing										
CBC with differential	X ³					X			X	
Chemistry Panels (Acute Care and Hepatic)	X ³					X			X	
Serum IFN gamma levels and antibody titers ⁶	X		X			X				
Pregnancy Testing ⁷	X						X		X	

- ¹ Investigational product may be instilled by clinic staff during the first three days of IP administration and will be prescribed as necessary to maintain the dosing regimen.
- ² BCVA with manifest refraction must be performed when scheduled and when there is a change in EVA of >10 E-ETDRS letters (> 0.20 logMAR) as compared with relevant baseline.
- ³ These procedures can be completed under NEI protocols 08-EI-0102 or 08-EI-0169 if performed within 9 days prior to Visit 000.
- ⁴ This test will be performed at least once but can be performed up to three times daily to assess for acute/subacute changes in macular cysts.

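### The only OCT fluid outcome names subretinal fluid, while the trial's target, entry rule and eye-selection rule concern macular cysts or intraretinal fluid; central thickness reflects the cysts only indirectly

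*Combined protocol and SAP*

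**What the plan says.** Section 7.2 states the efficacy aim first: "Evidence of efficacy will be assessed from any improvement in visual function and reduction in macular cystic changes", relative to baseline and to the untreated fellow eye. It then lists two OCT outcomes. The first is "Change in the maximum subretinal fluid volume as measured on OCT at all applicable time points compared to baseline". The second is "Change in the central retinal thickness as measured on OCT at all applicable time points compared to baseline". BCVA and microperimetry complete the list. A closing sentence adds that, for participants who enter on a CAI, the effect on their cystic changes will also be assessed; it names no measure.

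Elsewhere the protocol describes the target differently:

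- The Précis gives the objective as safety and potential efficacy of the drug "administered topically for macular edema/retinal schisis cysts in RCD and ESCS".
- Section 3.2.1 sets the entry rule: "The study eye must have macular cystic changes (>275 microns and/or disruption of foveal contour on OCT"). The Précis makes clear that the threshold is one of central macular thickness: ">275 microns central macular thickness and/or disruption of foveal contour".
- Section 3.2.3 gives the first rule when both eyes qualify: "The eye with more intraretinal fluid will be selected as the study eye".
- Appendix 1, footnote 4, says that OCT at baseline and Days 1 to 3 "can be performed up to three times daily to assess for acute/subacute changes in macular cysts".

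Section 8.0 plans descriptive, per-participant analysis without hypothesis tests. Section 8.1 tabulates the secondary outcomes as Section 7.2 defines them.

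**The concern.** The fluid outcome names a different retinal compartment from the one in which the participants' disease is described. An eye can enter because of cysts, be chosen because it has more intraretinal fluid, and then have its fluid response recorded in a space where the protocol never requires any fluid to be.

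This matters beyond tidiness because efficacy has a role in the trial. Section 2.0 puts possible efficacy in the primary objective. Section 4.1 has the review committee make a preliminary assessment of safety and efficacy after two participants per disease group reach Week 8, before enrollment resumes. Section 13.2 lets the committee or IRB recommend stopping for efficacy or lack of it. With up to five eyes per disease group described one by one, no model can make up for an uninformative measure. If the measure were redefined after the scans had been seen, the choice would be post hoc.

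**Working it through.** The plan gives no figure to reproduce: Section 8.2 has no sample size calculation, and Section 8.0 has no test. The check is a comparison of definitions.

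**Step 1. What each part of the protocol is about.**

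| Place | Quantity or lesion named |
|---|---|
| Précis, objective | macular edema or schisis cysts |
| Section 3.2.1, entry | cystic changes, by thickness and/or foveal contour |
| Section 3.2.3, eye selection | intraretinal fluid |
| Section 4.5.5 and end of 7.2, CAI users | cystic changes |
| Section 7.2, lead sentence | cystic changes |
| Section 8.0 | visual function and macular cysts |
| Appendix 1, footnote 4 | macular cysts |
| Section 7.2, fluid outcome | subretinal fluid |

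The last row stands alone. Apart from that row and titles in the reference list, subretinal fluid appears only in Section 1.0, in the account of how the retinal pigment epithelium (RPE) moves fluid. No section describes it as a feature of these participants' disease.

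**Step 2. Count of OCT outcomes in Section 7.2.** Total: 2. Worded as fluid: 1 (subretinal). Measuring cysts or intraretinal fluid directly: 0. Able to reflect the cysts indirectly: 1 (central retinal thickness).

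**Step 3. How the fluid outcome behaves.** Let S(t) be subretinal fluid volume and C(t) cyst volume at visit t. The outcome is S(t) − S(0), and C does not enter it. In an eye that never has subretinal fluid, S(0) = S(t) = 0, so the change is 0 − 0 = 0 at every visit, whether C falls, rises or stays level. In an eye with some subretinal fluid the outcome can move, but it still describes S and not C.

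**Step 4. How far central thickness fills the gap.** It can fall when central cysts shrink, and it matches the thickness limb of the entry rule. It is incomplete for two reasons. The entry rule says and/or, so an eye may qualify on foveal contour alone with thickness at or below 275 microns. A central measurement may also miss cysts outside the center.

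**Step 5. Which scan counts.** Appendix 1 schedules OCT at 7 visits: baseline, Days 1, 2 and 3, and Weeks 2, 5 and 8. Footnote 4, allowing one to three scans a day, is attached to 4 of them (baseline and Days 1 to 3). The other 3 (Weeks 2, 5 and 8) carry no such provision. The outcome refers to a maximum, but the protocol does not say whether that is taken over a day's scans, over positions within a scan, or over something else. Nor does it say which scan supplies the baseline value.

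**The case against.** Four points can be made for the plan.

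*The choice may be deliberate.* Section 1.0 rests the rationale on RPE control of subretinal fluid and on rodent work in which the drug reduced retinal detachment volume. That gives a subretinal measure a mechanistic basis, and no section says these eyes lack subretinal fluid. This stands as a reason to keep the measure as an extra outcome. It does not make the measure one of cystic change, which is what Section 7.2 says it will assess.

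*Thickness is listed next.* A reader might infer that the OCT outcomes as a whole cannot show an effect on the cysts. The documents do not support that: central retinal thickness is assessed at the applicable visits and can reflect cyst shrinkage. The Précis also mentions OCT and fluorescein angiography among the secondary outcomes, though it names no quantity to be read from them. What remains is that the link between the listed outcomes and the cysts is indirect and partial.

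*The outcome is secondary.* The primary outcome is adverse events and withdrawals, and Section 8.0 says the study is not designed to estimate changes in these outcomes accurately. No committee threshold is tied to the bullet, and the scans will exist in any case. This stands, and it limits the severity.

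*The scan count may not matter.* A reader might infer that extra baseline scans would inflate the baseline maximum and produce a spurious fall. That requires the maximum to be taken over a day's scans, the optional repeats to be done at baseline, and a repeat-scan error that the documents do not give. The fellow-eye comparison would offset part of any such effect if both eyes are scanned alike. No size can be put on it. Only the need to define the scan survives.

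**Conclusion.** The point holds in a limited form. The fluid outcome in Section 7.2 is wrong as written: it names subretinal fluid in a trial whose objective, entry rule, eye-selection rule and repeat-OCT purpose concern cysts or intraretinal fluid. It carries no information on change in the cysts. Central retinal thickness is the one listed OCT outcome that can reflect them, and only indirectly.

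The size is qualitative: 0 of 2 OCT outcomes measure the target directly. How many eyes would show a constant zero cannot be derived, since the documents give no frequency of subretinal fluid in either disease. The conclusion assumes that the bullet means what it says and that subretinal and intraretinal fluid are read as separate quantities. It does not touch the primary safety outcome, and no hypothesis test depends on it. It should be fixed, but it does not undermine the trial's main purpose.

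**What to change.** In Section 7.2, replace the subretinal bullet with, or add to it, change from baseline in intraretinal cystoid fluid volume on OCT in study and fellow eyes. If volume segmentation is unavailable, use cyst area or total macular volume. Define the OCT region and the reading method. Name the same measure for the assessment of participants on CAIs. Subretinal fluid volume may stay as an additional descriptive outcome, with a sentence giving the reason and saying what the maximum is taken over.

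State which scan supplies the value at each visit, and use the same number of scans at baseline and at follow-up. Same-day repeats can still be used to describe acute change.

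The change needs no new visit or scan. The cost is the amendment of the wording and some additional OCT segmentation or reading. The definition should be settled before the scans are read for efficacy.

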- ⁵ These procedures (skin biopsy for iPSCs and blood sample for iPSCs) may be performed at any study visit. The skin biopsy is only for participants who consent to providing skin biopsy samples for iPSC generation as this procedure is optional.
- ⁶ Collected samples will be shipped to Horizon Pharma (or their designee) for analysis.
- ⁷ This test is for women of childbearing potential only and they must have a negative test prior to the investigational product administration on enrollment day.
- ⁸ Visit records from a local ophthalmologist can substitute for the Week 52 safety visit if participant is unwilling or unable to come to NIH.

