2.0 VISUAL ACUITY TESTING USING THE EVA SYSTEM

It is essential to have standardized visual acuity measurements for each examination at each of the participating clinics to minimize the effects of acuity examiner and patient bias. Visual acuity testing is being performed with the Electronic Visual Acuity Tester (EVA) using a protocol called the Electronic ETDRS (E-ETDRS) Visual Acuity Testing Protocol. This protocol has been developed to provide a visual acuity score that is comparable to that using the manual testing protocol used in the Early Treatment of Diabetic Retinopathy Study (ETDRS). The ETDRS chart testing is used as a back-up in case the EVA is not functioning.

Visual acuity measurements for each eye are obtained by a certified visual acuity examiner before the patient's pupils have been dilated.

A. Electronic Visual Acuity Tester

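### Section 7.2 omits the scheduled Week 8 microperimetry, and its Week 52 BCVA change may set a local acuity against an EVA baseline

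*Combined protocol and SAP*

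**What the plan says.** **Microperimetry.** Section 7.2 lists "Change in central visual field sensitivity as measured by microperimetry testing at Day 2 and Week 5 compared to baseline". The flowsheet row in Appendix 1 reads "Microperimetry X ³ X X X"; read against the column headings, the four marks stand under Baseline, Day 2, Week 5 and Week 8. Section 8.1 tabulates the secondary outcomes by reference to Section 7.2.

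**BCVA.** Section 7.2 lists "Change in BCVA from baseline at all time points". The flowsheet row, "BCVA (EVA) X X X X X X X X", has eight marks: Baseline, Days 1, 2 and 3, and Weeks 2, 5, 8 and 52. For the last of these, footnote 8 says that "Visit records from a local ophthalmologist can substitute for the Week 52 safety visit" when the participant cannot or will not travel. Section 4.4 accepts that private physicians may test differently, while requiring documentation of the Week 52 flowsheet assessments. Manifest refraction is marked only at Baseline and Week 8. Footnote 2 adds it when EVA changes by more than 10 letters from baseline.

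**Acuity standard.** Appendix 4, Section 2.0 states: "It is essential to have standardized visual acuity measurements for each examination". It names the EVA as the method and the ETDRS chart as back-up.

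**The concern.** Of the four outcomes in Section 7.2, only microperimetry is tied to named visits, and the list is shorter than the schedule. No reason is given. Week 8 is also the visit after which the review committee makes its first judgement of safety and efficacy on the first four participants (Section 4.1). The study is unmasked, so if the plan is silent on Week 8, the choice to report those values stays open until they have been seen.

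The BCVA definition has the opposite problem: it takes in every visit, including one where the measurement method may change. A Week 52 value from a local chart, perhaps with a different refraction, minus an EVA baseline mixes true change with a change of method. With up to five participants per disease group, each presented individually, one non-comparable value is not averaged away.

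**Working it through.** The plan states no sample size calculation, alpha, power or effect size, so there is no figure to reproduce. The check compares the visits named in Section 7.2 with those marked in the flowsheet, then places the tests relative to dosing.

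**Step 1: visits scheduled and visits used, after baseline**

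| Outcome | Scheduled (Appendix 1) | Covered by Section 7.2 | Week 2 included? |
|---|---|---|---|
| Microperimetry | Day 2, Week 5, Week 8 (3) | Day 2, Week 5 (2) | Not scheduled |
| BCVA | Days 1, 2, 3; Weeks 2, 5, 8, 52 (7) | All 7 | Yes |
| OCT | Days 1, 2, 3; Weeks 2, 5, 8 (6) | All 6 | Yes |

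Microperimetry left out: 3 − 2 = 1 test, and 1/3 = 33%.

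**Step 2: timing relative to dosing**

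- The flowsheet gives "Target Day from Baseline 0 1 2 3 7 14 35 42 56 365", so Week 2 is Day 14, Week 5 is Day 35 and Week 8 is Day 56. The windows are ±5, ±7 and ±7 days.
- Section 4.5.3 has dosing start on Day 1 and end the day before the Week 2 visit. Last dosing day = 14 − 1 = Day 13, with range (9 − 1) to (19 − 1) = Day 8 to Day 18.
- Days from last dosing day to Week 5: 35 − 13 = 22, with range (28 − 18) to (42 − 8) = 10 to 34.
- Days from last dosing day to Week 8: 56 − 13 = 43, with range (49 − 18) to (63 − 8) = 31 to 55.
- If the two weeks of therapy in Section 4.4 are counted as 14 full days from Day 1, the last dosing day is Day 14 and the target intervals become 21 and 42 days.

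Microperimetry is thus measured on the second dosing day and then not until about three weeks after dosing ends. Adding Week 8 gives the outcome three post-baseline points but does not supply an end-of-treatment one.

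**Step 3: what a change of acuity method could do**

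The documents give no offset between local and study acuity. Purely as an assumption, take 5 to 10 letters. Footnote 2 equates 10 letters with 0.20 logMAR, or 0.02 per letter, so this is 0.10 to 0.20 logMAR. Section 6.0 gives a loss of more than 0.3 logMAR as an example of an adverse change to watch.

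- 0.10/0.3 = 1/3 and 0.20/0.3 = 2/3 of that value.
- Reaching 0.3 would need a further 0.10 to 0.20 logMAR of true change in the same direction.
- Within-eye change = true change + offset, so the offset stays in. Study-eye change minus control-eye change removes the part of the offset common to both eyes.

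**The case against.** The best defence is that little is lost. The Précis names microperimetry as a secondary outcome without limiting visits, and nothing says that Week 8 results will be withheld from the committee or from a report. That stands as far as it goes. But Section 8.1 points to Section 7.2 for the tables, and Section 7.2 excludes Week 8, so the mismatch still needs correcting.

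A reader might infer that the functional outcomes have no end-of-treatment measurement, or that Section 7.2 picked the wrong visits. The documents do not support either. BCVA is a functional outcome, is measured at Week 2 and is covered by Section 7.2. Day 2 and Week 5 are genuine microperimetry visits, so the list is incomplete rather than wrong. No text promises microperimetry at the end of dosing.

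A reader might also infer that a local chart at Week 52 could by itself produce or hide a safety signal. The assumed offset cannot exceed 0.3 logMAR alone, and Section 6.0 attaches no automatic action to that value. At an NIH visit, footnote 2 would call for refraction well before it. The trigger is worded for EVA, however, and does not clearly reach a local examination.

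Nor does Appendix 4 show a breach. Its sentence on standardization continues by referring to participating clinics, and an outside ophthalmologist is arguably not one in a single-center study. The flowsheet label could even be read as requiring the EVA locally, but Section 4.4 accepts differences in testing, and no text requires the EVA, a certified examiner or the study refraction there. What remains is a question of comparability: Week 52 is called a safety visit, yet Section 7.2 uses its acuity as an efficacy change.

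**Conclusion.** The point holds and is minor. Section 7.2 and the flowsheet disagree on Week 8 microperimetry, and the plan as written leaves one of three post-baseline tests out of its tables. The missing Week 2 test is a limit on interpretation: an effect on sensitivity present only during later dosing could go unseen, and an OCT change at Week 2 cannot be paired with sensitivity. Week 52 BCVA change may not be comparable with baseline for any participant seen locally. How many that will be, and by how much acuity would shift, cannot be known from the documents.

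Section 8.0 makes these analyses descriptive, by participant and without hypothesis tests, so no error rate or sample size is involved. The documents do not show that the primary outcome (IP-related adverse events and withdrawals) is distorted. The timing figures assume visits within the stated windows and the dosing end in Section 4.5.3.

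**What to change.** 1. In Section 7.2, change the microperimetry visits to Day 2, Week 5 and Week 8, or use the same all-applicable-visits wording as the OCT outcomes. This is wording only, since the test is already scheduled.
2. In Section 7.2, compute Week 52 BCVA change only from acuities measured under Appendix 4, whether by E-ETDRS or by the back-up ETDRS chart. A rule limited to E-ETDRS would wrongly drop a method the plan permits. List local acuities separately as safety information, with chart type and refraction status. The cost is fewer Week 52 BCVA change values.
3. In Section 8.1, add a sentence acknowledging that microperimetry has no end-of-treatment value. Moving the Week 8 test to Week 2 would supply one without adding a test, but it would give up the Week 8 value at the visit that precedes the committee's review. That is a trade-off for the investigators and is not needed to resolve the inconsistency.
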